Fatty acid supplementation will continue until the baby is full term (40 adjusted weeks of age). If the infant is discharged before he/she is full-term, the infant will be sent home with a bottle of the fatty acid oral solution for the infant to continue daily until he/she is full-term (40 weeks of age). The infant's nutritional needs will be carefully monitored by his/her doctor and nutritionist per NICU protocols.

To monitor the amount of fatty acid nutrition getting into the blood, we will check the infant's blood. As much as possible, we will coordinate the study blood collection at the same time as the routine NICU blood draws. We will collect 1.3 milliliters of blood at 4 different times spread apart while the infant is in the hospital. At each time point, we will collect about 1/4 teaspoon of blood, for a total of about 1 teaspoonful.

The blood draws will occur as the following four time points:

- Blood draw T0= Prior to parenteral nutrition, within 1st 3 days of life. This blood collection should be

taken from cord blood. If cord blood is not available, sample will be collected from a UAC, UVC, or peripheral blood draw concurrent with SOC.

- Blood draw T1= 5 days after parenteral nutrition is started; grace period +/-3 days therefore total 2-8 days after parenteral nutrition started.
- Blood draw T2= 5 days after enteral nutrition full feeds have arrived; grace period +/-3 days therefore total 2-8 days after full enteral nutrition arrived.
- Blood draw T3= Prior to discharge from hospital coinciding with time that ROP may be present, ≥ 35 weeks adjusted age.

This blood will be used for looking at what new genes (mRNA) the infant is making and to check how many and what kind of fatty acids the infant has in the blood. Before testing, the blood will be stored in a storage facility at the UCSD Department of Ophthalmology Blood Bank and labelled with a barcode without the infants' personal information. This is not the infant's DNA, and no DNA will be isolated or tested. Samples will be stored for 10 years. After this time point, all samples will be destroyed if not used by that time. If the parent decides to withdraw consent the blood samples that were already drawn will be destroyed, however, any previously obtained data from sample testing will be kept.

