Eye exams: All infants will get eye exams according to standard NICU protocols. Serial eye exams will be performed according to the usual intervals, which is until retinal vascularization has matured or active ROP has stabilized, usually at 1-2 months post-term. The area of vascularized retina, clock hours of neovascularization, and amount of retinal vascular dilation and tortuosity will be measured by indirect ophthalmoscopy in all infants at each clinical exam by an ophthalmologist masked to the treatment group. Stage of retinopathy of prematurity and need for ROP treatments will be measured at 40 weeks gestation plus or minus three weeks and followed over time. Infants with ROP will be monitored over time for longer term visual and anatomic outcomes. For both groups, infants will have SOC eye examinations prior to discharge around 40 weeks GA (≥ 38 wks GA). For both groups, if infant is discharged prior to 38 weeks GA, we will collect follow-up data from their outpatient follow-up eye exam from UCSD or other provider

Nutrition: Omegaven has been approved by the FDA for use in children and infants with parenteral nutrition associated liver disease (PNALD). In this study we intend to use Omegaven under an IND exemption to study the use of the drug in reducing the incidence and severity of retinopathy of prematurity (ROP). Our aim is to differentiate the phospholipid profiles and gene expression pathways of at-risk very low birth weight infants with and without treatment with Omegaven® (high n-3 fish oil supplement) and to establish whether omega-3 fatty acid supplementation in extremely low birth weight infants will reduce the incidence and severity of retinopathy of prematurity (ROP). The study intervention “drug product” has been used in the neonatal population via the same route of administration safely for other disease indications internationally and nationally including here at University of California San Diego. This investigation does not significantly increase the risk or decrease the acceptability of risk of our study population.

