Our primary analytic approach will use generalized linear mixed models (GLMM). These methods will address problems of missing data, variable timing of the subject visits, and other possible unintended violations of design. Although our retention and follow-up plan is designed to minimize missing data, an advantage of the GLM models is that they allow us to maximize statistical power by not excluding subjects with some missing data. More specifically, GLM assumes that the data can be missing at random (MAR) or missing completely at random (MCAR). The benefit of this assumption is with a repeated measure problem (e.g., longitudinal data) you can still analyze data from all subjects, even if some have missing data (assumed MAR or MCAR). Mixed regressions will also allow us to estimate an intercept and slope for each patient based on all available data for that individual augmented by the data from the entire sample, with two random effects being used to model time trends (i.e., a random intercept and a linear trend). Further details of selected analyses related to each outcome are provided next.

For Outcome (a-b), the primary outcome is DHA at a specified period of time (i.e. 40 weeks) to assess the basic fatty acids. Outcome (a) posits that patients in Group 1 will differ from those in Group 2 with respect to i) DHA

ii) EPA iii) AA iv) bioactive metabolites. To assess Outcome (a) (i.e. to evaluate the effects of group, time, and their interaction on the change from baseline DHA measurements), a mixed effects model with group (IV Omegaven then PO baby fish oil or Intralipid), time, and group by time interaction as fixed effects, and random intercept and slope to account for within subject correlation. We expect that the interaction in question will be significant.

For Outcome (c), we hypothesize that Group 1 and Group 2 will have a different severity stage of ROP. To assess Outcome (c), we will use a *Mixed-effects ordinal logistic regression model* with severity stage of ROP after 40 weeks (Stage I, II, III, IV, V) as the outcome variable. The same fixed and random effects mentioned above will be used in evaluating Outcome(c).

All statistical analyses will be performed using SAS software version 9.3 (SAS Institute, Cary, North Carolina, USA).

[figure not shown]
Power Calculations

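### The primary DHA outcome and its power figure are set at 40 weeks, but the last blood sample is taken before discharge, from 35 weeks, and none is planned afterwards

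*Combined protocol and SAP*

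**What the plan says.** All of this is in Section 9 of the combined protocol and SAP.

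- **Endpoint (Statistical Analysis).** "the primary outcome is DHA at a specified period of time (i.e. 40 weeks"). The same paragraph then sets out a model to evaluate group, time and "their interaction on the change from baseline DHA measurements".
- **Outcome Measures.** Outcome 1 is a change in fatty acid concentrations at multiple time points, with no 40-week anchor.
- **Power Calculations.** The calculation uses a pre-post difference in DHA, 42 versus 27 µmol/L, taken from a cited study. The time point of those figures is not stated. The Figure 1 caption refers to DHA at 40 weeks.
- **Blood draws.** "We will collect 1.3 milliliters of blood at 4 different times spread apart while the infant is in the hospital". T3 is "Prior to discharge from hospital coinciding with time that ROP may be present", at 35 weeks adjusted age or later, with no upper age limit. The Lipidomics paragraph also places the last sample before discharge.
- **Discharge before term.** "If the infant is discharged before he/she is full-term, the infant will be sent home with a bottle of the fatty acid oral solution". Parents in the Omegaven arm are contacted weekly between discharge and 40 weeks.
- **Eye outcome, for comparison.** Stage and "need for ROP treatments will be measured at 40 weeks gestation plus or minus three weeks". The text expects an examination before discharge around 40 weeks (38 weeks or later), and collects outpatient examination data if discharge comes before 38 weeks.
- **Model.** Mixed models are chosen partly to cope with "variable timing of the subject visits", "with two random effects being used to model time trends (i.e., a random intercept and a linear trend").

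**The concern.** DHA is the only outcome with a power calculation, and its named time point does not match the sampling schedule. The eye outcome has a window around 40 weeks and a route for collecting data after early discharge. DHA has neither. An infant still in hospital at 40 weeks could be sampled then, but nothing requires it. An infant discharged earlier has no 40-week DHA value by design.

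The plan also describes the endpoint in three ways: a level at 40 weeks, a change from baseline over time, and a pre-post difference at an unstated time. An analyst would have to choose among them, possibly after seeing data. A result reported as DHA at 40 weeks could then rest partly on a modelling choice instead of on samples.

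**Working it through.** **1. The plan's own power figure.** Inputs from Power Calculations: two-sided alpha 0.05, two-sample t-test, 40 infants split equally (n = 20 per group), difference 42 − 27 = 15 µmol/L, common SD from 5 to 15.

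Noncentrality = 15 / (SD × √(2/20)), df = 38, critical t = 2.024. At SD 15 this is 15 / (15 × 0.3162) = 3.162.

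| SD | Power |
|---|---|
| 15 | 86.9% |
| 13 | 94.5% |
| 11 | 98.7% |
| 9 or less | above 99.9% |

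The stated power of over 80% at SD 15 reproduces. The calculation contains no time variable. It applies at 40 weeks or at T3 alike, provided the same difference and SD hold there.

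**2. Endpoint against schedule.** The named time is 40 weeks. T3 is allowed from 35 weeks, so the last DHA value can precede the endpoint by up to 40 − 35 = 5 weeks. For an infant discharged before 38 weeks the gap exceeds 2 weeks. The documents do not say how many infants this affects.

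**3. What the planned model can estimate.** The fixed effects are group, time and their interaction. The coding of fixed time is not stated.

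- Categorical by visit: the last estimable contrast is T3, and there is no 40-week estimate.
- Continuous and linear: a 40-week contrast can be calculated, but for infants discharged early it extends the line beyond their last sample.

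**4. How large an extrapolation error could be (illustration only).** Assumptions:

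- birth at 28 weeks (the average in the cited study);
- T0 at 0.2 weeks after birth, T1 at 0.9, and T2 at 2, 3 or 4 (not in the documents);
- every infant sampled at the same T3 age;
- a true group difference of 0 at T0 and 15 from T1 through 40 weeks.

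Fit a least-squares line to the group difference at T0–T3 and read it at 12 weeks after birth (40 weeks).

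Worked case, T2 at 4 weeks and T3 at 7 weeks (35 weeks adjusted): mean time 3.025, mean difference 11.25, Sxy = 42.375, Sxx = 29.2475, slope = 42.375 / 29.2475 = 1.449. Value at 40 weeks = 11.25 + 1.449 × (12 − 3.025) = 24.3, about 62% above 15.

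| T3 age (weeks) | Fitted difference at 40 weeks, over T2 = 2 to 4 |
|---|---|
| 35 | 22.9 to 24.3 |
| 36 | 20.6 to 21.9 |
| 37 | 19.0 to 20.0 |
| 38 | 17.7 to 18.6 |
| 40 | 16.1 to 16.6 |

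Three checks limit what this shows:

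- With T3 at exactly 40 weeks nothing is extrapolated, yet the line is still 7% to 11% too high, because a straight line misfits a step. With T3 at 38 weeks it already reads 16.3 to 16.8 at T3 itself.
- If the response is change from baseline with rows T1–T3 only, the profile is 15, 15, 15. The slope is then zero and the 40-week value is exactly 15.
- If the true trend is linear, the error is zero.

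**The case against.** Several counter-arguments have force.

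- **Discharge may usually be near term.** The eye-examination text treats an examination before discharge at 38 weeks or later as the ordinary case and earlier discharge as the exception. T3 has no upper age limit, so some samples may fall close to 40 weeks. This stands. A reader might infer that 40-week DHA will be missing for most or all infants, but the documents give no discharge ages and do not support that.
- **The mixed model handles variable timing.** It does use every available sample, including those of infants without a T3. It cannot observe a value that was never scheduled, so the endpoint remains unsecured for infants discharged early.
- **The linear trend belongs to the random effects.** This also stands. A reader might infer that the plan commits to extrapolating a straight line to 40 weeks. It does not: the coding of fixed time is open, and no 40-week prediction is described.
- **Level versus change is minor.** Under randomisation both have the same expected between-group difference. The inconsistency matters for clarity more than for the size of the effect.

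Two further readings are tempting and unsupported. One is that the trial is underpowered: if only observed 40-week values counted, 17 per group would give 80.7% and 16 per group 78.1%, but the plan does not restrict the analysis in that way and the share sampled at 40 weeks is unknown. The other is that the DHA effect will be overstated by a given percentage, which depends entirely on coding and on the true trend.

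**Conclusion.** The mismatch is real and should be fixed. The plan names and powers a 40-week DHA outcome, while its schedule guarantees only a pre-discharge sample from 35 weeks onward. For infants discharged before term, the endpoint as worded is not secured. This conclusion rests on the text alone and is firm.

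Its numerical consequence is not firm. The number of infants affected is unknown. The error in a 40-week estimate runs from zero (linear trend, or change from baseline at T1–T3 with a constant difference) to about 62% in one constructed case: T0 kept as an outcome row, a step profile, and every T3 at 35 weeks. Part of even that figure is straight-line misfit and not extrapolation.

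The power arithmetic is sound. What needs correcting is the time point attached to it. The trial remains analysable.

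**What to change.** - Define the primary endpoint once, as the change in DHA from T0 to T3, with T3 the last pre-discharge sample at or after 35 weeks adjusted age.
- Test it as the between-group contrast at T3 in the planned mixed model, with visit as a categorical factor. Infants without a T3 stay in through their earlier samples.
- Align Outcome Measures, Statistical Analysis and Power Calculations. Retitle Figure 1 to T3, and state the time point of the borrowed 42 and 27 µmol/L.
- Report by arm the age at T3 and the number of infants without a T3.
- Add a sensitivity analysis adjusting for age at T3.

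Adjustment for baseline DHA and for gestational age at birth (the randomisation factor) is an optional extra, not needed to remove the contradiction.

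**Cost.** Wording only. No extra blood is drawn, and the stated power is unchanged if the planning difference and SD hold at T3.

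**Downsides.** The endpoint no longer refers to exactly full term, and supplementation at home up to 40 weeks is not reflected in it. T3 timing depends on discharge, which follows randomisation under an unblinded NICU team and could differ by arm. The reporting and sensitivity analysis above would show whether that matters. If 40 weeks must remain the endpoint, the schedule needs a 40-week sample that includes infants already discharged.

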The investigational drug pharmacy (IDS) will obtain the Omegaven and dispense it to the nurse for administration in a separate line than the rest of the nutrition (amino acids, sugars, etc). The NICU nutritionist will optimize the total nutritional calories to the infant per NICU protocols. The IDS pharmacist, nutritionist, and NICU team will not be blinded to ensure that the infant in the Omegaven group meets all the nutritional requirements as determined by the NICU neonatology attendings and fellows involved in the study. The ophthalmology team will be blinded to the treatment group to prevent any potential for bias during the eye exam.

Outcome Measures:

Outcome 1: Change in concentrations of basic fatty acids (EPA, DHA, and AA) and their bioactive metabolites will be assessed at multiple time points.

Outcome 2: Change in mRNA expression of TNF- α , PPAR- γ , and VEGF at multiple time points.

Outcome 3: Severity stage of ROP in Group 1 compared to Group 2. This will be assessed at the time of ROP screening (approximately 31 weeks), and the outcome will be measured at approximately 40 weeks adjusted age. The stage of ROP at 40 weeks adjusted will be used for statistical analyses.

Safety:

A data safety monitoring board (DSMB) will be established to monitor the safety of enrolled infants in the study as well as identifying the efficacy of the treatment at ongoing intervals. The DSMB will meet after the first 5 infants are enrolled and then regularly at multiple intervals during the study. Clinical safety assessments will occur during the hospital admission including vital signs, weight, physical exam and laboratory assessments of triglycerides. The neonatologist will review the assessments and determine if the subject should remain in the study or be removed.

Statistical Analysis

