The power calculations that follow were conducted using the software PASS and are based on two-sided tests, with a 0.05 type I error rate. A sample size N=40 was assumed. Power calculation for the primary outcome is presented below.

Power for Outcome (a)

Outcome (a) tests the effect that Group 1 has a different average DHA measurement compared to Group 2. The power calculation for Outcome (a) was based on a two-sided two-sample t-test with a dependent continuous variable (i.e. pre-post difference in DHA measurements) on a categorical independent variable (i.e. Group 1 and Group 2) with a sample size of 40 total subjects. These subjects were equally distributed between each of the two treatment groups. In Pawlik et al. (2013), the mean pre-post difference were 42 $\mu\text{mol/L}$ for patients in Group 1 and 27 $\mu\text{mol/L}$ for patients in Group 2. Following Pawlik et al.'s sampling distribution, we also considered 6 common standard deviation estimates for the power calculation 5, 7, 9, 11, 13, and 15. It should be noted that as the common standard deviation within the group decreases, the group will yield greater power to detect an intervention group effect. As illustrated by the curve in Figure 1, we will have over 80% power to detect a mean difference among the 2 groups of average DHA measurements with a common standard deviation of 15, which is the smallest difference that we can detect with the proposed sample size.

Figure 1: Power for Group Effect on the DHA at 40 weeks.

Note: Even though the data analysis plan relies on longitudinal methods (GLMM), due to unavailability of estimates for repeated measures, the above power calculations were based on a single time point method (two sample t-test). However, the use of a longitudinal method generally results in an increase in power, therefore we believe we will retain sufficient power for the study based on the methods proposed here.

In addition, we have determined that in order to reach a targeted sample size of 40 subjects completing treatment, we will need approximately 60 subjects enrolled to this protocol. This is our target accrual.

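### The primary outcome (DHA at 40 weeks) has no stated deciding contrast: power is shown for one pre-post difference, while the model singles out the group-by-time interaction

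*Combined protocol and SAP*

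**What the plan says.** All of this is in section 9 of the combined protocol and SAP.

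- **Outcome Measures**, first item: "Change in concentrations of basic fatty acids (EPA, DHA, and AA) and their bioactive metabolites will be assessed at multiple time points".
- **Statistical Analysis**, endpoint: "the primary outcome is DHA at a specified period of time (i.e. 40 weeks" (closing bracket omitted).
- **Statistical Analysis**, model: fixed effects for group, time and group-by-time, used "to evaluate the effects of group, time, and their interaction on the change from baseline DHA measurements". The random part is described as "with two random effects being used to model time trends (i.e., a random intercept and a linear trend". Of the three fixed effects, one is singled out: "We expect that the interaction in question will be significant".
- **Power Calculations**: a two-sided two-sample t-test on the pre-post DHA difference, 40 infants split equally, mean changes 42 and 27 µmol/L, and six SDs from 5 to 15. The text introduces this as a test of whether average DHA differs between groups. Figure 1 is captioned "Power for Group Effect on the DHA at 40 weeks".
- **Note under Figure 1**: "the above power calculations were based on a single time point method (two sample t-test", because repeated-measures estimates were not available. It then argues that "the use of a longitudinal method generally results in an increase in power, therefore we believe we will retain sufficient power".
- **Laboratory blood draws**: four samples, T0 to T3. The last is taken before discharge, at 35 weeks adjusted age or later. No draw is fixed at 40 weeks.

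**The concern.** Three different contrasts are described for one primary outcome: a difference at the final time, a difference in average DHA, and a group-by-time interaction. The plan does not say which one decides. It also does not say whether fixed time is linear or categorical, or whether T0 DHA is a response row or only the value subtracted.

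Two readings of the response are open. Under the first, raw DHA at T0 to T3 is modelled and the interaction carries the treatment effect. Under the second, change from baseline at T1 to T3 is modelled, and the interaction measures only how the gap moves after T1. An early gap is plausible on the protocol's own evidence. Section 7 reports higher DHA on treatment at 7 and 14 days in the earlier fish-oil trial, although it does not say what followed.

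The stake is twofold. If the interaction is read as decisive, a real final difference of the size the trial is powered for could be missed. If nothing is fixed, the term and the time coding can be chosen after the data are seen.

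**Working it through.** **1. The plan's own figure.** Inputs from Power Calculations: 20 per arm, difference 42 − 27 = 15, SD 15, two-sided 0.05. Noncentrality = 15 / (15 × √(2/20)) = 3.162 on 38 df, which gives power 86.9%. At SD 13 it is 94.5%, and at SD 11 it is 98.7%. The stated figure of over 80% is reproduced.

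**2. When the contrasts coincide.** With raw DHA at baseline and final visit only, the group-by-time coefficient is (final − baseline in Group 1) − (final − baseline in Group 2). That is exactly the quantity powered. The contrasts separate because there are four draws.

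**3. Assumptions for four draws.** The documents give no trajectory, draw days or covariance. I assume draws at days 0/5/30/63, a final gap of 15 and Var(T3 − T0) = 15² = 225. A share f of that variance comes from the random slope, with f from 0 to 0.75. Residual variance is (1 − f) × 225/2, and slope variance is f × 225/63².

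**4. Raw DHA, linear days, full gap from T1.** Mean day is 24.5; deviations are −24.5, −19.5, 5.5 and 38.5; Sxx = 2493.
- Slope difference = 15 × (−19.5 + 5.5 + 38.5)/2493 = 0.1474 per day.
- f = 0: slope SD = √(112.5/2493) = 0.2124; noncentrality = 0.1474/(0.2124 × 0.3162) = 2.195; power 57.1%.
- f = 0.75: slope SD = √(168.75/3969 + 28.125/2493) = 0.2319; noncentrality 2.010; power 50.0%.
- REML fits of the random intercept and slope model (1,000 simulated trials each) gave 46.5% at f = 0, 51.9% at f = 0.5 and 50.5% at f = 0.75. The simulation error is about 1.6 points, so the shortfall at f = 0 is real. A likely reason is that a straight line does not fit a step, which inflates the residual. When the gap truly grows linearly, both methods give 93.2% at f = 0. I therefore quote about 46–57%.

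**5. Change from baseline at T1 to T3, linear days.** Mean day is 32.67; deviations are −27.67, −2.67 and 30.33; Sxx = 1692.7.
- Gap 15/15/15: 15 × (−27.67 − 2.67 + 30.33) = 0. There is no interaction, so power is 5%.
- Gap 7.5/15/15: slope difference = 207.5/1692.7 = 0.1226; at f = 0, noncentrality = 0.1226/(0.2578 × 0.3162) = 1.504; power 31.1%.

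**6. Categorical interaction, raw DHA.** F test on 3 and 36 df with noncentrality λ = d′W⁻¹d, where d holds the three differences from T0 and W is their covariance times 2/20. For the constant gap, λ runs from 15.0 to 44.8. For linear growth it runs from 12.6 down to 10.5.

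**7. Results.** Power in %, over f = 0 to 0.75, final gap 15 throughout:

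| Gap at T1/T2/T3 | Final-visit difference | Average T1–T3 change | Interaction: raw, linear days | Interaction: raw, visit number | Interaction: raw, categorical | Interaction: change score, linear days |
|---|---|---|---|---|---|---|
| 15/15/15 | 86.9 | 96.5–99.9 | 50.0–57.1 (REML low 46.5) | 79.1–83.2 | 88.3 to over 99 | 5.0 |
| 7.5/15/15 | 86.9 | 88.2–98.8 | 78.2–84.8 | 89.8–92.7 | 85.1–98.7 | 31.1–34.3 |
| 7.5/11.25/15 | 86.9 | 80.8–96.8 | 74.8–81.8 | 85.1–88.6 | 75.2–91.0 | 33.6–37.0 |
| Linear growth | 86.9 | 49.9–75.0 | 88.6–93.2 | 88.0–91.1 | 73.5–81.4 | 81.2–85.5 |

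The final-visit column is constant by construction, since that contrast depends only on the final gap and its SD.

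**8. Sensitivity of the analytic 50–57%.** It becomes 62–69% at SD 13, 76–83% at SD 11 and 90–95% at SD 9. With T1 at day 2–8, T2 at day 14–45 and T3 at day 35–119, it ranges from 26% to 78%.

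**The case against.** The plan is not silent. It names the endpoint. The power section describes a group comparison of average DHA, and the figure caption places a group effect at 40 weeks. The interaction sentence states an expectation, not a decision rule. A random intercept and slope per infant suits raw DHA over time, so the change-from-baseline wording may be shorthand for the contrast that was powered. The t-test and mixed-model mismatch is disclosed. Under categorical coding the early constant gap costs nothing: power is 88% or more.

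Much of this stands. It rules out three stronger conclusions that a reader might draw.

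- *That the trial is underpowered, or the stated power wrong.* The figure is correct for its test, and most shapes with raw DHA stay near it.
- *That the plan commits to the interaction as the decisive test.* It does not; it leaves the choice open.
- *That power is really 5%.* This needs the change-score reading and a gap that is complete about five days into parenteral nutrition and then exactly constant. Section 7 reports higher DHA at 7 and 14 days, not a complete gap, and supplementation continues towards 40 weeks.

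What the objection does not do is name the contrast. The average-DHA sentence adds a third candidate. The disclosure explains why a t-test was used, but a gain in power for one contrast does not transfer to another. Categorical coding is not uniformly better either: it gives about 74–81% if the gap grows linearly.

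**Conclusion.** The concern holds as a specification gap in the primary analysis, and should be fixed. The final-visit difference, the average group effect and the interaction are all open. For the same 15 µmol/L final gap at SD 15, power depends on which is taken: 87% for the final-visit difference, about 50% to over 99% for the average effect, about 46–93% for the linear-day interaction on raw DHA, and 31–37% for the change-score interaction if half the gap is present at T1. The assurance that a longitudinal method adds power is therefore not guaranteed.

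The 87% rests on the plan's own inputs. Everything else rests on assumed draw days, trajectories and covariance, and on the largest of the plan's six SDs. These figures show how far the answer can move, and are not an estimate of expected loss. The sample size is not in question.

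**What to change.** - Name the group difference in DHA at the final visit, adjusted for T0 DHA, as the single primary contrast. Estimate it with T0 as a covariate, or with a repeated-measures model of DHA at T0 to T3 that has categorical visit and a common T0 mean in both arms. The second form keeps infants with no T0 sample.
- Make the interaction and the averaged group effect secondary. Keep the planned random-slope model, with age at draw, as a sensitivity analysis.
- Replace the sentence on longitudinal methods with power for the named contrast: 87% unadjusted on the stated inputs. Baseline adjustment raises it by an amount that depends on an unknown correlation (88–97% under the correlations I assumed).
- State whether the final visit is T3 as drawn or 40 weeks, and reconcile Statistical Analysis and Power Calculations with the blood-draw schedule.

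Cost: SAP wording and a standard SAS model. T0 DHA is already collected and N stays at 40. The downsides are less use of exact draw times, which the plan gives as a reason for mixed models, and a few more covariance parameters with about 40 infants. The sensitivity analysis covers the first. A simpler covariance structure with Kenward-Roger degrees of freedom, stated in advance as a fallback, covers the second.

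### The primary DHA analysis of change from baseline makes no adjustment for T0 DHA, which gives up precision, and it leaves unclear what happens to infants without a T0 sample

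*Combined protocol and SAP*

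**What the plan says.** All of this is in section 9 of the combined protocol and SAP.

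- **Model.** For Outcome (a), a mixed-effects model is to be used "to evaluate the effects of group, time, and their interaction on the change from baseline DHA measurements". The fixed effects are group, time and their interaction, with a random intercept and slope. No T0 DHA term is listed.
- **Outcome wording.** Outcome 1 under Outcome Measures is a change in concentration. The Statistical Analysis text, however, names DHA at 40 weeks as the primary outcome.
- **Power.** The power calculation uses a two-sample t-test on the "pre-post difference in DHA measurements".
- **Baseline sample.** T0 is drawn "Prior to parenteral nutrition, within 1st 3 days of life". Cord blood is preferred, with a line or peripheral sample as the fallback.
- **Missing data.** The mixed model is justified partly because "you can still analyze data from all subjects, even if some have missing data".

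The plan does not state whether the response is change at T1 to T3 or DHA at T0 to T3. It gives no rule for an infant without T0.

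**The concern.** A raw change score subtracts the whole of T0, so the coefficient on T0 is fixed at 1. The best coefficient is the regression slope of follow-up on T0, which is usually below 1 when the two are weakly related. T0 is a sample from the first days of life, possibly cord blood. The last draw comes weeks later, after parenteral and then enteral feeding and, in one arm, fish oil. A modest correlation is therefore plausible, though the documents do not report one. Subtracting all of T0 then adds noise to the declared primary outcome of a trial planned around 40 completers.

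A second issue depends on how the text is read. If change is the response, an infant without T0 has no value at any visit, and that infant's later samples go unused.

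**Working it through.** **Inputs from the Power Calculations text.** The tests are "based on two-sided tests, with a 0.05 type I error rate". "A sample size N=40 was assumed", and "These subjects were equally distributed between each of the two treatment groups", so n = 20 per arm. On group means, "the mean pre-post difference were 42" µmol/L for Group 1 and 27 for Group 2, a difference of 15. The largest SD of change considered is 15.

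**Assumptions, not in the documents.** The correlation rho between T0 and follow-up DHA, the ratio k of the T0 SD to the follow-up SD, and the proportion of infants without T0.

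**1. The plan's own figure.** The SE of the difference is 15 × √(2/20) = 4.74, so the noncentrality is 15/4.74 = 3.16. The noncentral t with 38 df gives 86.9% (normal approximation 88.5%). The plan's claim of power above 80% reproduces.

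**2. T0 adjustment with equal variances (k = 1).** If s is the SD at each time, the variance of change is 2s²(1 − rho) and the residual variance after regression on T0 is s²(1 − rho²). Their ratio is (1 + rho)/2, so the residual SD is 15 × √((1 + rho)/2). Power uses the noncentral t with 37 df.

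| rho | residual SD | power | infants a change-score analysis needs to match 40 adjusted, 40 × 2/(1 + rho) |
|---|---|---|---|
| 0.1 | 11.1 | 98.6% | 73 |
| 0.3 | 12.1 | 96.8% | 62 |
| 0.5 | 13.0 | 94.5% | 53 |
| 0.7 | 13.8 | 91.6% | 47 |
| 0.9 | 14.6 | 88.5% | 42 |

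The unadjusted figure throughout is 86.9%.

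**3. Unequal variances.** The ratio becomes (1 − rho²)/(1 + k² − 2·k·rho), with the SD of change held at 15.

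- k = 0.75, rho = 0.5: 0.75/0.8125 = 0.923, residual SD 14.4, power 89.3%.
- k = 0.5, rho = 0.3: 0.91/0.95 = 0.958, residual SD 14.7, power 88.2%.
- k = 0.5, rho = 0.5: 0.75/0.75 = 1, residual SD 15, power 86.8%. There is no gain, and one degree of freedom is spent.

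The ratio never exceeds 1, because its denominator minus its numerator is (k − rho)². Apart from that degree of freedom, adjustment does not lose.

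**4. Does the choice of response matter for precision?** This uses generalised least squares for the T3 difference in change, with four visits, time as visits, compound symmetry and complete T0. The SE is 4.74 with change as the response, and also 4.74 with DHA at T0 to T3 and a free baseline mean per arm. With a common baseline mean it is 3.82, 4.11 and 4.37 at rho 0.3, 0.5 and 0.7. The loss is the same under either reading.

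**5. Infants without T0, if change is the response.** Step 1 is repeated with fewer infants per arm.

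| assumed share of the 40 without T0 | n per arm | power |
|---|---|---|
| 10% | 18 | 83.0% |
| 15% | 17 | 80.7% |
| 20% | 16 | 78.1% |
| 30% | 14 | 72.1% |

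With DHA at T0 to T3 as the response, these infants stay in. At 20% missing and rho 0.5, on the normal approximation, power is 80.7% for the change score, 83.7% for DHA with free baselines and 94.7% with a common baseline mean.

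**The case against.** The strongest reply is that the plan never says the response is DHA minus T0. The mention of change describes the effects to be evaluated. A random intercept and slope model with a group-by-time interaction can be fitted to DHA at T0 to T3, where the interaction is itself the group difference in change. The primary outcome is described as DHA at 40 weeks, and the plan wants to keep infants with incomplete data. A reader might infer that the analysis drops every infant without T0. The documents do not establish this: it follows only under one of two readings, and the other fits the stated missing-data aim better. This part of the objection stands. It does not remove the precision loss, which is the same under both readings (step 4).

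A reader might also infer that power falls below the plan's claim. That needs an assumed share without T0 of about 20%, taken from the 40, under the change-score reading. The protocol provides a fallback source for T0 and plans to enrol 60 to obtain 40 completers. At 10% and 15% missing, power is still above 80%.

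Finally, the gain from adjustment is of unknown size, because rho and the variance ratio are not given. Mean DHA is expected to rise by 27 to 42 µmol/L, so follow-up variance could exceed T0 variance, and in some such cases the gain is nil. This stands too, and is why a range is shown.

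**Conclusion.** The point holds as one of efficiency and specification. No T0 adjustment is planned for the primary DHA comparison, although the sample is already collected. Under equal variances, adjustment would raise power from 86.9% to between 88.5% (rho 0.9) and 98.6% (rho 0.1). Under some unequal variances the gain is small or absent. The cost of adjusting is at most one degree of freedom.

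The planned comparison is not biased, since randomisation protects it, and the stated power is met when T0 is complete. The loss of infants without T0 is conditional on change being the literal response. That reading would contradict the plan's own missing-data rationale, so the text needs to settle it. The missing-T0 rates used here are illustrative.

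**What to change.** In the Statistical Analysis text for Outcome (a), state that DHA at T0, T1, T2 and T3 is the response in a longitudinal model with one common T0 mean for both arms and group-by-visit effects from T1 onward. Name the T3 group difference as the primary contrast. Every infant with any DHA sample then contributes, and T0 is adjusted for within the model. Use the same form for EPA and AA.

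Adding T0 DHA as a plain covariate to a change-score model would recover the precision but would still exclude infants without T0. It is adequate only with a pre-specified method for missing T0.

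The cost is a change of wording in the analysis plan. No extra samples, visits or infants are needed.
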